11.5. Appendix 5: Derived and Transformed Data

11.5.1. General

Multiple Measurements at One Analysis Time Point

- Mean of the measurements will be calculated and used in any derivation of summary statistics but if listed, all data will be presented.
- Subjects having both High and Low values for Normal Ranges at any post-baseline visits for safety
 parameters will be counted in both the High and Low categories of "Any visit post-baseline" row of
 related summary tables. This will also be applicable to relevant Potential Clinical Importance summary
 tables.

Study Day

- Calculated as the number of days from randomisation date:
 - Ref Date = Missing
 - → Study Day = Missing
 - Ref Date < Randomisation Date → Study Day = Ref Date Randomisation Date
 - Ref Date ≥ Randomisation Date → Study Day = Ref Date (Randomisation Date) + 1

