- Summary = Represents TFL related to any summaries (i.e. descriptive statistics) of the observed raw data.
- Individual = Represents FL related to any displays of individual participant observed raw data.
- 1. Listings will include participant's numbers for individual AE's & AE system organ classes, preferred terms and verbatim text.
- 2. Chemistry summaries will include both changes from baseline & emergent results by PCI criteria.
- 3. Listings and summaries for ECGs and vital signs include treatment emergent PCI results

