7.3. Clinical Laboratory Analyses

Laboratory results will be included in the reporting of this study for hematology, coagulation, clinical chemistry, and urinalysis.

Protocol-specified clinical laboratory tests will be summarized using descriptive statistics. The statistics will be presented for each scheduled assessment during the study and change from baseline to each scheduled assessment. Presentations will use SI Units, as provided by the labs or converted from values in other units. Clinical laboratory data collected during unscheduled visits of study conduct that were not required per protocol, such as for special testing to evaluate an AE, will be listed and not summarized.

Based upon laboratory normal ranges, the laboratory test results will be categorized according to the normal range as low (below the lower limit), normal (within the normal range) and high (above the upper limit). Summary statistics for change from baseline based on PCI will also be tabulated. The details of the planned displays are in Appendix 11: List of Data Displays.

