11.3. Appendix 3: Study Phases and Treatment Emergent Adverse Events

11.3.1. Study Phases

Assessments and events will be classified according to the time of occurrence relative to dosing.

| Study Phase | Definition |
|----------------|---|
| Pre-Treatment | Date ≤ Study Treatment Start Date |
| On-Treatment | Study Treatment Start Date < Date ≤ Study Treatment Stop Date |
| Post-Treatment | Date > Study Treatment Stop Date |

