| | Worst Post Baseline | n Increase<=30 30 <increase<=60 increase="">60</increase<=60> | 12 12(100%) 0 | 6 6(100%) 0 | 6 6(100%) 0 |

Example SAFE_T7
Protocol: 205822
Population: Safety

rotocol: 205822 Page 1 of 1

Table X
Frequency of Maximum ECG Values by PCI Category

| ECG Test | Visit | Category | Placebo (N=12) | 1 capsule - Single Dose | Single Dose |
|------------------------------------|------------------------|--|-------------------------------|----------------------------|------------------------|
| PR Interval, Aggregate (msec) | BASELINE | n | 12 | 6 | 6 |
| nggregate (mete) | | Value<110 110<=Value<=220 Value>220 | | 0 6(100%) 0 | 0 6(100%) 0 |
| | WORST POST BASELINE | n Value<110 110<=Value<=220 Value>220 | - | 6 0 6(100%) 0 | 6 0 6(100%) 0 |
| QRS Duration, Aggregate (msec) | SCREENING | n | 12 | 6 | 6 |
| 1199209000 (111000) | | Value<75 75<=Value<=110 Value>110 | , , | 0 6 (100%) 0 | 0 6(100%) 0 |
| | WORST POST BASELINE | n Value<75 75<=Value<=110 Value>110 | 12 0 11 (92%) 1 (8%) | 6 0 6(100%) 0 | 6 0 6(100%) 0 |
| QTcB Interval, Aggregate (msec) | SCREENING | n | 12 | 6 | 6 |

205822

| | Value<=450 | 11 (92%) | 6 (100%) | 6 (100%) |
|------------|--|----------|----------|----------|
| | 450 <value<480< td="">1 (8%)	0	0	</value<480<> | 1 (8%) | 0 | 0 |
| | 480<=Value<500 | 0 | 0 | 0 |
| | Value>=500 | 0 | 0 | 0 |
| WORST POST | n | 12 | 6 | 6 |
| BASELINE | Value<=450 | 11 (92%) | 5 (83%) | 6 (100%) |
| | 450 <value<480< td="">1 (8%)	1 (17%)	0	</value<480<> | 1 (8%) | 1 (17%) | 0 |
| | 480<=Value<500 | 0 | 0 | 0 |
| | Value>=500 | 0 | 0 | 0 |

Repeat for QTcF

Note: Percentages may not add up to 100 for QRS Duration and PR Interval as there is a possibility of a patient being counted under both low and high categories.

205822

Example : PK_T1 Page 1 of n : 205822

Population : Systemic PK

Table 3.1.13
Summary of Assessment of Dose Proportionality (Part 1 and Part 2)

| | | | Slope | | | _ | | | |
|-----------|-------|---|----------|----|--------|----------|----|--------|----------------|
| Parameter | Study | n | Estimate | SE | 90% CI | Estimate | SE | 90% CI | Coefficient of |
| | Day | | | | | | | | Determination |

Note(s): CI = confidence interval; SE = standard error.

Source: SAS Output XX

205822

Example : PK_T2 Page 1 of n

Protocol : 205822 Population : Systemic PK

Table 3.1.16 Summary of Assessment of Steady State (Part 1 and Part 2)

| | | | Slope | Slope | | | | |

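### Emergent PCI results are promised but not defined, and the ECG shell for absolute limits cannot yield an emergent count

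*SAP*

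**What the plan says.** Section 7 makes the promise in the notes to Table 3. Note 2 reads "Chemistry summaries will include both changes from baseline & emergent results by PCI criteria", and note 3 reads "Listings and summaries for ECGs and vital signs include treatment emergent PCI results". Neither note says what makes a laboratory, ECG or vital-sign value emergent. Section 7.2 and Section 11.3.2 deal with emergence for adverse events only.

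Three other places bear on the question:

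- Section 11.3.1: "Assessments and events will be classified according to the time of occurrence relative to dosing". The rule uses dates. Pre-treatment runs up to and including the treatment start date; on-treatment begins after it and ends on the stop date.
- Section 11.5.1: "Subjects having both High and Low values for Normal Ranges at any post-baseline visits for safety" parameters are counted under both headings of the any-post-baseline row. It adds: "This will also be applicable to relevant Potential Clinical Importance summary" tables.
- Section 11.11, shell SAFE_T7, "Frequency of Maximum ECG Values by PCI Category", used for Tables 3.43 to 3.45. It has one block of pre-treatment counts and a separate block of worst post-baseline counts for each ECG interval. The pre-treatment block is labelled as baseline for PR but as screening for QRS and QTcB. Section 5.2.1 displays ECG baseline as Day 1 pre-dose.

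Appendix 7 contains two kinds of limit. Some are absolute (PR, QRS, QTc, blood pressure, heart rate, liver tests, most chemistry). Others are changes from baseline (haematocrit and haemoglobin decreases, creatinine, QTc increase, vital-sign changes).

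**The concern.** Safety is a primary objective, and the PCI tables are where a reader looks for shifts in ECG, vital signs and chemistry. If emergence is promised, the reader will take a post-baseline PCI count as a count of new abnormalities. In SAFE_T7 it is not: someone whose QRS or QTc was beyond the limit before the first dose, and stays there, is counted in the post-baseline block.

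Part 1 Cohort A makes this worse. Its active participants receive three regimens in sequence (60 mg and 120 mg single doses, then 30 mg BID), and Section 7 summarises safety by dose. One persistent pre-existing abnormality could therefore appear under three active doses. With columns this small, a single participant is a visible percentage.

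**Working it through.** The plan states no figure to reproduce. The check sets the texts side by side and then does simple counting on the shell.

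**1. Can the date rule supply the definition?** In Part 2 Cohort A there is one dose, so treatment start date = stop date = Day 1.

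- On-treatment requires start < date ≤ stop, i.e. Day 1 < date ≤ Day 1. No date satisfies this.
- Day 1 satisfies date ≤ start, so the post-dose ECGs and vital signs scheduled at 0.25, 1, 2, 4, 8 and 12 h (Appendix 2) are classed as pre-treatment.
- In the repeat-dose cohorts the post-dose values of the first dosing day fall the same way.

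So the rule misplaces the first-day post-dose values, and a separate definition is needed.

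**2. Does Section 11.5.1 supply it?** No. It says how to count a participant with values on both sides of a range. It neither includes nor excludes those already abnormal at baseline.

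**3. Can the emergent count be read from SAFE_T7?** Let b be the number beyond the limit pre-treatment, p the number beyond it post-baseline, and N the column size. From the two margins alone, the number newly beyond the limit lies between max(0, p − b) and min(p, N − b). For QTcB above 450 msec in the shell's dummy data:

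| Column | N | b | p | As tabulated | Newly beyond limit |
|---|---|---|---|---|---|
| Placebo | 12 | 1 | 1 | 1/12 = 8.3% | max(0, 0) = 0 to min(1, 11) = 1, i.e. 0% to 8.3% |
| First active | 6 | 0 | 1 | 1/6 = 16.7% | max(0, 1) = 1 to min(1, 6) = 1, i.e. 16.7% |

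No dummy count falls in the two higher QTcB categories, so here newly beyond 450 and a worse category than before mean the same. These are illustrative numbers and show only the mechanism: once anyone is abnormal beforehand, the margins do not fix the emergent count. Because the QTcB row is labelled as screening, b is also not shown as the Section 5.2.1 baseline.

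**4. Weight of one participant.** 100/6 = 16.7 points at N=6 and 100/12 = 8.3 points at N=12. In Part 1 Cohort A the same person could add 16.7 points under each of three active doses.

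**The case against.** The strongest reply is that emergent may simply mean arising after dosing. The post-baseline block of SAFE_T7 would then deliver it, and the gap would be an undefined term rather than a contradiction. It is indeed an undefined term. But the only timing rule for assessments fails on the first dosing day, and a finding present before treatment and unchanged after it is not emergent in any useful sense.

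Several limits on the point stand:

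- A reader might infer from Section 11.5.1 that all PCI and High/Low counts disregard baseline. The text does not support that. The sentence is a double-counting rule, and the change-from-baseline criteria already use baseline, including those behind Tables 3.46 to 3.48.
- No emergence is promised for haematology. Nor is it promised for the low/normal/high categories of Section 7.3, which have no table in the display list.
- The laboratory and vital-sign PCI tables use standard shells (LB17, VS2) that are not shown and may condition on baseline.
- Listings 55 to 57 (ECG) and 65 to 67 (vital signs) give all values for any participant with a PCI value, so single cases can be traced.
- A reader might also infer that COPD participants would look less tolerant than healthy ones. The plan does not support this either. Safety displays are split by part, Part 2 has its own placebo group, the planned healthy-versus-COPD displays are pharmacokinetic, and no baseline prevalence is given for either population.

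**Conclusion.** The point holds for the absolute ECG limits. SAFE_T7, followed as written, does not deliver the emergent result promised in Section 7, and the emergent count cannot in general be recovered from the table. For chemistry and vital signs it holds only in that the promised term is undefined; whether the tables themselves are affected depends on shells not shown.

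The size is 16.7 points per affected participant at N=6 or 8.3 at N=12, possibly repeated across three doses in Part 1 Cohort A. This assumes shell column sizes like those reported and an abnormality that persists after dosing. How many participants would be affected cannot be said from the documents. The study is descriptive and tests no hypothesis, and the listings allow tracing, so no inference is invalidated. Still, this is a summary of a primary objective that should be corrected before reporting.

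**What to change.** 1. In Sections 11.5.1 and 11.7, define treatment-emergent PCI for absolute limits as a post-baseline value in a worse PCI category than the same participant's baseline category. Count a missing baseline as emergent, in line with the worst-case convention for adverse events in Section 7.2. Where a parameter has a low and a high limit (PR, QRS), apply the definition to each direction separately.
2. Lay SAFE_T7 out as baseline category by worst post-baseline category, and label the pre-treatment side consistently as the Section 5.2.1 baseline (Day 1 pre-dose) rather than screening. State which record serves as baseline in the repeat-dose cohorts. Their schedule in Appendix 2 places replicate ECGs and vital signs on Day −1 and times the Day 1 reading 2 h after the morning dose. Without that clarification the missing-baseline convention could flag participants wrongly.
3. Apply the same definition to the chemistry (3.22 to 3.24) and vital-sign (3.55 to 3.57) PCI tables unless LB17 and VS2 already condition on baseline.
4. Leave the change-from-baseline criteria as they are.

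The cost is SAP wording and shell edits, with no new data. The downside is some sparse cells in columns of 6 to 12.

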11.5.2. Study Population

Demographics

Age

- GSK standard IDSL algorithms will be used for calculating age where birth date will be imputed as follows:
 - Any subject with a missing day will have this imputed as day '15'.
 - Any subject with a missing date and month will have this imputed as '30th June'.
- Birth date will be presented in listings as 'YYYY'.

Body Mass Index (BMI)

• Calculated as Weight (kg) / [Height (m)²]

Extent of Exposure

Number of days of exposure to study drug will be calculated based on the formula:

Duration of Exposure in Days = Treatment Stop Date - (Treatment Start Date) + 1

- Subjects who were randomized but did not report a treatment start date will be categorised as having zero days of exposure.
- The cumulative dose will be based on the formula:

Cumulative Dose = Sum of (Number of Days x Total Daily Dose)

If there are any treatment breaks during the study, exposure data will be adjusted accordingly.

11.5.3. Safety

Laboratory Parameters

- If a laboratory value which is expected to have a numeric value for summary purposes, has a non-detectable level reported in the database, where the numeric value is missing, but typically a character value starting with '<x' or '>x' (or indicated as less than x or greater than x in the comment field) is present, the number of significant digits in the observed values will be used to determine how much to add or subtract in order to impute the corresponding numeric value.
 - Example 1: 2 Significant Digits = '< x ' becomes x 0.01
 - Example 2: 1 Significant Digit = '> x' becomes x + 0.1

Example 3: 0 Significant Digits = '< x' becomes x - 1

11.6. Appendix 6: Reporting Standards for Missing Data

11.6.1. Premature Withdrawals

| Element | Reporting Detail |
|---------|--|
| General | Subject study completion (i.e. as specified in the protocol) was defined as completion of all visits of the study including the follow-up visit. Withdrawn subjects may be replaced in the study. All available data from subjects who were withdrawn from the study will be listed and all available planned data will be included in summary tables and figures, unless otherwise specified. |

11.6.2. Handling of Missing Data

| Element | Reporting Detail |
|----------|---|
| General | Missing data occurs when any requested data are not provided, leading to blank fields on the collection instrument: |
| | These data will be indicated by the use of a "blank" in subject listing displays. Unless all data for a specific visit are missing in which case the data are excluded from the table. |
| | Answers such as "Not applicable" and "Not evaluable" are not considered to be missing data and should be displayed as such. |
| Outliers | Any subjects excluded from the summaries and/or statistical analyses will be documented along with the reason for exclusion in the clinical study report. |

11.6.2.1. Handling of Missing and Partial Dates

| Element | Reporting Detail |
|---|--|
| General | Partial dates will be displayed as captured in subject listing displays. |
| Adverse Events | The eCRF allows for the possibility of partial dates (i.e., only month and year) to be recorded for AE start and end dates; that is, the day of the month may be missing. In such a case, the following conventions will be applied for calculating the time to onset and the duration of the event: Missing Start Day: First of the month will be used unless this is before the start date of study treatment; in this case the study treatment start date will be used and hence the event is considered On-treatment as per Appendix 3: Study Phases and Treatment Emergent Adverse Events. Missing Stop Day: Last day of the month will be used, unless this is after the stop date of study treatment; in this case the study treatment stop date will be used. Completely missing start or end dates will remain missing, with no imputation applied. Consequently, time to onset and duration of such events will be missing. |
| Concomitant Medications/ Medical History | Partial dates for any concomitant medications recorded in the CRF will be imputed using the following convention: If the partial date is a start date, a '01' will be used for the day and 'Jan' will be used for the month If the partial date is a stop date, a '28/29/30/31' will be used for the day (dependent on the month and year) and 'Dec' will be used for the month. The recorded partial date will be displayed in listings. |

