11.3.2. Treatment States for Adverse Events Data

| Treatment State | Definition |
|-----------------|--|
| Pre-Treatment | AE Start Date < Study Treatment Start Date if AE start time not available; else |
| Pre-mealment | AE Start Date time < Study Treatment Start Date time |
| On-Treatment | If AE onset date is on or after treatment start date & on or before treatment stop date. |
| | Study Treatment Start Date ≤ AE Start Date ≤ Study Treatment Stop Date |
| Post-Treatment | If AE onset date is after the treatment stop date. |
| | AE Start Date > Study Treatment Stop Date |
| Onset Time | If Treatment Start Date > AE Onset Date = AE Onset Date - Treatment Start Date |
| Since 1st Dose | If Treatment Start Date ≤ AE Onset Date = AE Onset Date - Treatment Start Date +1 |
| (Days) | Missing otherwise. |
| Duration (Days) | AE Resolution Date – AE Onset Date + 1 |
| Drug-related | If relationship is marked 'YES' on CRF OR value is missing. |

NOTES:

• If the study treatment stop date is missing then the AE will be considered to be On-Treatment.

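### The AE partial-date rules place events from an earlier month on treatment and cut event ends at the last dose; a minor correction is needed

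*SAP*

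**What the plan says.** SAP Section 11.6.2.1 starts from the fact that the day may be missing while month and year are known: "The eCRF allows for the possibility of partial dates (i.e., only month and year) to be recorded for AE start and end dates". It states the purpose of its rules: "the following conventions will be applied for calculating the time to onset and the duration of the event".

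- **Start day missing.** The default is the first day of the recorded month. Where that day precedes the first dose, an override takes over: "in this case the study treatment start date will be used and hence the event is considered On-treatment".
- **Stop day missing.** "Last day of the month will be used, unless this is after the stop date of study treatment". Where it is later, the end of treatment replaces it.

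Section 11.3.2 sets the treatment states. An AE is Pre-Treatment under the condition "AE Start Date < Study Treatment Start Date if AE start time not available", with a date-time comparison where the time is known. It is Post-Treatment if onset is after the treatment stop date. Duration is resolution date minus onset date plus 1.

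Section 7.2 sends partial AE dates to these rules. It keeps the worst-case assignment (treatment emergent) for the rare event whose emergence cannot be assessed.

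**The concern.** The start override suits the month in which dosing began: the order of onset and first dose is then unknown, and a cautious choice is reasonable. As written, it applies to every earlier month too. There the recorded month already shows that onset preceded dosing, so emergence can be assessed and the worst-case principle of Section 7.2 does not apply.

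The stop cap treats the last dose as the end of observation. The schedule in Section 11.2.1 places AE review at a follow-up visit 30±2 days after the last dosing day, and Section 11.3.2 has its own Post-Treatment state. The plan therefore expects events that begin or end after the last dose, and the cap cannot represent them.

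At stake are a possible false count in the treatment-emergent tables of a study with AEs as a primary endpoint, and impossible or shortened durations in derived data.

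**Working it through.** The plan gives no figure to reproduce, so the written rules were applied to dates.

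**Inputs from the SAP.**
- Start, stop and partial-date rules: Section 11.6.2.1.
- Treatment states and duration = resolution − onset + 1: Section 11.3.2.
- Screening up to 30 days (Part 1) or 45 days (Part 2) before Day 1, SAE review at screening, AE and SAE review at follow-up 30±2 days after the last dosing day: Section 11.2.1.

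**Assumed example dates.** Repeat dosing on Days 1 to 14 = 10 to 23 March; single dose on 10 March; a 28-day February. The sign of the errors does not depend on these choices.

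**1. Start rule, earlier month.** An SAE is recorded as starting in February, day missing. The first of the month, 1 February, is before 10 March, so the start becomes 10 March and the event is On-Treatment. The latest possible true onset is 28 February, 10 days before dosing, so every possible onset day is Pre-Treatment under Section 11.3.2. If the event has a full stop date of 25 February, its duration is −13 + 1 = −12 days.

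**2. Stop rule, onset after the last dose.** Let onset be k days after the last dose (k ≥ 1). A stop month that contains or follows the onset ends on or after the onset day, hence after the last dose, so the cap always applies. Duration = (last dose) − (last dose + k) + 1 = 1 − k.
- k = 1: 0 days
- k = 10: −9 days
- k = 30: −29 days

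Single dose 10 March, onset 14 March, stop recorded as March: k = 4, duration 1 − 4 = −3 days. The possible range is 1 day (stop 14 March) to 18 days (stop 31 March).

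**3. Stop rule, onset on treatment and continuing.** Last dose 23 March, onset 20 March, stop recorded as April. The stop is set to 23 March and the duration is 3 + 1 = 4 days. The earliest possible stop, 1 April, gives 12 + 1 = 13 days. Follow-up falls on 22 April ± 2 days, so at the latest on 24 April, which gives 35 + 1 = 36 days. The range is therefore 13 to about 36 days if the end is capped at follow-up.

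**4. Where the errors surface.** Section 11.10.5 lists treatment-emergent tables (3.1-3.2, 3.7-3.8), which a false On-Treatment status could enter. No listed AE table is titled for duration or time to onset.

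**The case against.** The strongest case on the other side concerns reach, and most of it stands.

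- **Few events.** This is a single-centre study with participants admitted to the clinic over the dosing period, so days should seldom be missing. The screening schedule marks SAE review but not AE review, so an earlier-month start would mainly be an SAE between screening and dosing.
- **Direction.** The start error adds an event and hides none.
- **SAE reporting.** A reader might infer that SAE reporting is corrupted. The documents do not support that: Tables 3.13-3.15 and Listings 32-34 are not limited by title to treatment-emergent events, so such an SAE appears whatever state is imputed.
- **Durations.** A reader might also infer that planned safety summaries of duration are wrong. None is listed, and Section 11.6.2.1 shows partial dates in listings as captured, so the recorded month stays visible.

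It could further be argued that the rules serve only time to onset and duration, not treatment state. That does not stand: the start rule itself concludes that the event is On-treatment and refers to Appendix 3 for that status.

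An upper limit of 42 days in the third check (stop on 30 April: 41 + 1) is also tempting. It needs a resolution after the follow-up visit and does not fit a cap at follow-up.

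**Conclusion.** Both rules give wrong results as written. The start rule contradicts Section 11.3.2 for any AE with a recorded month wholly before dosing. The stop rule gives a zero or negative duration (1 − k days) for every post-treatment AE with a missing stop day, and shortens AEs that continue past the last dose when the recorded stop month ends after it.

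The practical size is small. The start error could add rare false events to Tables 3.1-3.2 and 3.7-3.8. The stop error affects derived durations only. The documents do not support reading this as a threat to the primary safety conclusions. It is a minor correction.

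This rests on a literal reading of Section 11.6.2.1. The number of partial dates is not given and is assumed to be low. The calendar dates are illustrative.

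**What to change.** **Start day missing.** Use the treatment start date only when the recorded month and year equal those of treatment start and any known stop date is not before treatment start. Otherwise use the first of the recorded month. Earlier months, and events known to have ended before dosing, are then Pre-Treatment; later months are classified On- or Post-Treatment under Section 11.3.2.

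The stop-date check is needed. With dosing from 10 March, a start in March and a full stop date of 5 March, a month condition alone would still give a start of 10 March and a duration of −5 + 1 = −4 days. With the check, the start is 1 March, the event is Pre-Treatment and the duration is 4 + 1 = 5 days.

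**Stop day missing.** Use the last day of the recorded month, capped at the follow-up or last-contact date instead of the treatment stop date, and never before AE onset.

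The cost is a short rewording of the two rules in Section 11.6.2.1 and a small change to the AE derivation. No new data are needed.
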